8.3.1. Exploratory Analysis

Descriptive statistics will be provided for the total number of days spent in the hospital/ in the ICU/ on mechanical ventilation from the time of post-randomization for the MITT population. Number of days on mechanical ventilation will be analyzed in the subgroup of ventilated subjects at baseline.

Provides a list of the total number of days in the hospital after randomization, the total number of days in the intensive care unit, and the total number of days on mechanical ventilation after randomization for the subjects, sorted in ascending order by subject number.

8.4. Other Efficacy Endpoints

Other efficacy analysis will be summarized based on the MITT Population.

8.4.1. Chest Imaging

A by-subject listing of chest imaging will be provided by visit in chronological order.

8.4.2. Oxygenation Status

Descriptive statistics will be provided by treatment group for Oxygenation status related test as follows:

- Baseline value
- Values at each postbaseline visit (nominal visit)
- Change from baseline at each postbaseline visit

A baseline value will be defined as the last available value collected on or prior to the date/time of first dose of study drug. Change from baseline for a postbaseline visit will be defined as the postbaseline value minus the baseline value. Oxygenation status related test measured at unscheduled visits before first dose will be included for the baseline value selection.

Descriptive analysis of oxygenation status will be performed using the following units: PaO₂ (mmHg), FiO₂ (unitless), O₂ saturation (%), PH (unitless) and PaO₂/FiO₂ (unitless).

A list of subjects' oxygenation status will be provided in chronological order of visit, in ascending order of subject number.

8.4.3. Sequential Organ Failure Assessment (SOFA) score

Descriptive statistics will be provided by treatment group for total SOFA Score as follows:

- Baseline value
- Values at each postbaseline visit (nominal visit)
- Change from baseline at each postbaseline visit

BA baseline value will be defined as the last available value collected on or prior to the date/time of first dose of study drug. Change from baseline to a postbaseline visit will be defined as the postbaseline value minus the baseline value. Total SOFA Score measured at unscheduled visits before first dose will be included for the baseline value selection.

A by-subject listing of SOFA score will be provided by visit in chronological order.

8.4.4. Glasgow Coma Score (GCS)

Descriptive statistics will be provided by treatment group for total Glasgow Coma Score as follows:

- Baseline value
- Values at each postbaseline visit (nominal visit)
- Change from baseline at each postbaseline visit

A baseline value will be defined as the last available value collected on or prior to the date/time of first dose of study drug. Change from baseline to a postbaseline visit will be defined as the postbaseline value minus the baseline value. Total Glasgow Coma Score measured at unscheduled visits before first dose will be included for the baseline value selection.

A by-subject listing of Glasgow Coma Scale will be provided by visit in chronological order.

8.4.5. HABP/VABP Clinical Signs/Symptoms

The proportions of subjects with HABP/VABP clinical signs/symptoms assessment at all visits will be provided for each treatment group in the MITT populations.

A by-subject listing of HABP/VABP clinical signs/symptoms will be provided by visit in chronological order.

9. SAFETY ANALYSIS

9.1. Adverse Events and Deaths

9.1.1. Adverse Events Dictionary

Clinical and laboratory adverse events (AEs) will be coded using the current version of MedDRA. System organ class (SOC), high-level group term (HLGT), high-level term (HLT), preferred term (PT), and lower-level term (LLT) will be provided in the AE dataset.

9.1.2. Adverse Events Severity

Adverse events are graded by the investigator as Grade 1, 2, 3, 4, or 5 according to terminology criteria specified in the protocol. The severity grade of events for which the investigator did not record severity will be categorized as “missing” for tabular summaries and data listings. The missing category will be listed last in summary presentation.

9.1.3. Relationship of Adverse Events to Study Drugs

Related AEs are those for which the investigator selected “Definitely related”, “Probably related” or “Possibly related” on the AE CRF to the question of “Relationship to study drug”. Events for which the investigator did not record relationship to study drug will be considered related to study drug for summary purposes. However, by-subject data listings will show the relationship as missing.

9.1.4. Serious Adverse Event

Serious adverse events (SAEs) will be identified and captured as SAEs if the AEs met the definitions of SAEs that were specified in the study protocol.

9.1.5. Treatment-Emergent Adverse Events

9.1.5.1. Definition of Treatment-Emergent Adverse Events

Treatment-emergent AEs are defined as any AEs with an onset time at or after the study drug start time.

9.1.5.2. Incomplete Dates

If the date/time of occurrence of the AE was incomplete and the date/time of the end of the AE was not earlier than the date/time of the first administration of the study drug, the date/time of occurrence, month, and year (or month and year only, and so on if the date/time was not documented) were used to determine whether or not the AE was a therapeutic-phase adverse event. The AE was considered a treatment-phase adverse event if both of the following criteria were met:

- Date/time of AE occurrence is the same as or after the month and year (or year) of the date/time of the first dose of study medication

If the onset and end date/time of an AE are missing completely, or if the onset date/time is missing and the end date/time is later than the date of the first dose, then the AE will be considered a therapeutic period adverse event. In addition, an AE will be considered a treatment-period

adverse event if the AE's onset date/time is missing and the end date/time is incomplete but the month and year (or year only if the month is not recorded) are the same as or after the date of the first dose.

9.1.6. Summary of Adverse Events and Deaths

Treatment-emergent AEs will be summarized based on the Safety Population.

9.1.6.1. Summary of Treatment-Emergent Adverse Events Incidence

A summary table of TEAEs by treatment group is given, and the number of cases and percentage of subjects experiencing at least 1 TEAE by SOC, PT, and treatment group will also be summarized for the following classifications:

- TEAE
- Drug-related TEAE
- TEAE with Grade 3 or higher
- Drug-related TEAE with Grade 3 or higher
- Serious TEAE
- Drug-related Serious TEAE
- Drug discontinuation due to TEAE
- Drug discontinuation due to Drug-related TEAE
- Study discontinuation due to TEAE
- Study discontinuation due to Drug-related TEAE
- TEAE with incidence greater than 1% (based on total group)
- Drug-related TEAE with incidence >1% (based on total group)
- TEAE leading to death
- Drug-related TEAE leading to death

The number and percentage of subjects who experienced at least 1 TEAE will be provided and summarized by SOC, PT, severity grade and treatment group:

- TEAE
- TEAE with Grade 3 or higher
- Drug-related TEAE
- Drug-related TEAE with Grade 3 or higher
- Serious TEAE
- Drug-related Serious TEAE

Multiple events will be counted only once per subject in each summary. Adverse events will be summarized and listed first in descending order of the XNW4107 group frequency within each SOC and PT, if SOC or PT frequency are same, alphabetic order will be used within each SOC or PT.

For summaries by severity grade, the most severe grade will be used for those AEs that occurred more than once in an individual subject during the study.

In addition, data listings will be provided for the following:

- All AEs, labeled as TEAE or not
- TEAE with Grade 3 or higher
- Serious TEAE
- Drug interruption due to TEAE
- Drug discontinuation due to TEAE
- Study discontinuation due to TEAE
- AE leading to death

9.1.6.2. Subgroup analysis of treatment-emergent adverse events

The incidence of TEAE and deaths mentioned in Section 9.1.6.1 will be summarized in the safety population in a manner similar to that described in Section 8.1.2.4 and analyzed by the following subgroups.

- Age (< 65 years and \geq 65 years)
- Gender (male and female)
- Region (China and the rest of the world)
- Type of infection at baseline (non-ventilated HABP and ventilated HABP)
- Baseline APACHE II total score (<15 and \geq 15)
- Baseline eGRF (<30 mL/min, 30 to <60 mL/min, 60 to <90 mL/min, 90 to <150 mL/min, 150 to < 250 mL/min and \geq 250 mL/min)
- Baseline liver function (abnormal and normal)

9.2. Laboratory Evaluations

Laboratory data collected during the study will be analyzed and summarized using both quantitative and qualitative methods. Summaries of laboratory data will be provided for the Safety Population and will include data collected throughout the study. The analysis will be based on values reported in system international units. When values are below the LOQ, they will be listed as such, and the closest imputed value will be used for the purpose of calculating summary statistics as specified in Section 3.6.

Laboratory evaluations will be summarized based on the safety population.

A by-subject listing for laboratory test results will be provided by visit in chronological order for hematology, biochemistry, coagulation and urinalysis separately.

9.2.1. Summary of Numerical Laboratory Results

Descriptive statistics will be provided by treatment group for selected laboratory test as follows:

- Baseline value
- Values at each post-baseline visit (nominal visit)
- Change from baseline at each post-baseline visit

A baseline laboratory value will be defined as the last measurement obtained on or prior to the date/time of first dose of study drug. Change from baseline to a postbaseline visit will be defined as the visit value minus the baseline value. Laboratory test results measured at the unplanned visit prior to the first dose of medication will be included in the selection of the baseline value.

9.2.2. Shifts Relative to the Baseline Values

A shift table of the investigators' assessment of laboratory results at each visit (nominal visit) compared with baseline values will be presented by treatment group using the following categories: normal; abnormal, not clinically significant; abnormal, clinically significant; or missing. The number and percentage of subjects in each cross-classification group of the shift table will be presented. Subjects with a missing value at baseline or postbaseline will not be included in the denominator for percentage calculation.

9.2.3. Liver-related Laboratory Evaluations

Liver-related abnormalities after initial study drug dosing will be examined and summarized using the number and percentage of subjects who were reported to have the following laboratory test values for postbaseline measurements:

- Aspartate aminotransferase (AST): (a) > 3 times of the upper limit of reference range (ULN); (b) > 5 x ULN; (c) > 10 x ULN; (d) > 20 x ULN
- Alanine aminotransferase (ALT): (a) > 3 x ULN; (b) > 5 x ULN; (c) > 10 x ULN; (d) > 20 x ULN
- AST or ALT: (a) > 3 x ULN; (b) > 5 x ULN; (c) > 10 x ULN; (d) > 20 x ULN
- Total bilirubin: > 2 x ULN
- Alkaline phosphatase (ALP) > 1.5 x ULN
- AST or ALT > 3 x ULN and total bilirubin: (a) > 1.5 x ULN; (b) > 2 x ULN

For individual laboratory tests, subjects will be counted once based on the most severe postbaseline values. For both the composite endpoint of AST or ALT and total bilirubin, subjects will be counted once when the criteria are met at the same postbaseline visit date. The denominator is the number of subjects in the Safety Analysis Set who have no missing postbaseline values of all relevant tests at the same postbaseline visit date. A listing of subjects who met at least 1 of the above criteria will be provided.

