11. Subject is receiving hemodialysis or peritoneal dialysis or micro-dialysis or continuous venovenous hemofiltration or continuous venovenous hemodialysis.
12. Subject is anticipated to be treated with any of the following medications during the course of study therapy:
 - a. Valproic acid or divalproex sodium (or has used valproic acid or divalproex sodium in the 2 weeks prior to screening)

- 
- b. Concomitant systemic (IV or oral) Gram-negative antibacterial agents in addition to those designated in the study treatment groups
 - c. Concomitant systemic (IV or oral) antifungal or antiviral therapy for the index infection of HABP/VABP.
13. Life expectancy is <3 days.
 14. Subjects in refractory septic shock, defined as persistent hypotension despite adequate fluid resuscitation and vasopressive therapy at the time of randomization.
 15. Subjects with 1 or more of the following laboratory abnormalities in baseline specimens: aspartate aminotransferase, alanine aminotransferase $>3 \times$ the upper limit of normal (ULN), total bilirubin level $>2 \times$ ULN (except for isolated hyperbilirubinemia due to known Gilbert's disease), neutrophils <500 cells/mm³, platelet count $<40,000$ /mm³.
 16. History of active liver disease or cirrhosis.
 17. Subjects with an APACHE II score of >30 .
 18. A female who is pregnant or breastfeeding or has a positive pregnancy test as screening.
 19. Subject is participating in any clinical study of any investigational medication (i.e., non-licensed medication) during the 30 days prior to randomization. COVID-19 vaccines that are given under emergency use authorization are not considered investigational agents.
 20. Any other condition or prior therapy, which, in the opinion of the investigator, would make the subject unsuitable for this study.

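### The liver table's ALP row, and its bilirubin row for subjects with Gilbert's disease, count elevations already present at entry as abnormalities after dosing

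*SAP*

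**What the plan says.** SAP 9.2.3 states that "Liver-related abnormalities after initial study drug dosing will be examined and summarized using the number and percentage of subjects", namely those "who were reported to have the following laboratory test values for postbaseline measurements". Among the criteria are "Alkaline phosphatase (ALP) > 1.5 x ULN", "Total bilirubin: > 2 x ULN" and the combined criterion "AST or ALT > 3 x ULN and total bilirubin: (a) > 1.5 x ULN; (b) > 2 x ULN". AST, ALT and the two taken together each have rows above 3, 5, 10 and 20 x ULN. For single tests, "subjects will be counted once based on the most severe postbaseline values". The section has no baseline condition and no baseline category. It adds a listing of subjects who met a criterion.

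Protocol 4.2, item 15, excludes "Subjects with 1 or more of the following laboratory abnormalities in baseline specimens: aspartate aminotransferase, alanine aminotransferase" above 3 x ULN, and total bilirubin above 2 x ULN except in isolated hyperbilirubinemia from known Gilbert's disease. Its other limits concern neutrophils and platelets. ALP is not mentioned. Item 16 excludes active liver disease or cirrhosis but sets no laboratory value.

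**The concern.** The table is introduced as showing abnormalities after the first dose, but for ALP the rule cannot tell a new elevation from one the subject brought into the trial. Take a subject at 1.8 x ULN before dosing and at most 1.7 x ULN afterwards: the value fell, yet the subject enters the ALP row. A Gilbert's subject at 2.3 x ULN throughout enters the bilirubin row in the same way.

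The plan expects abnormal liver tests at entry, since SAP 5.2 defines a baseline category of abnormal liver function that includes ALP. It also uses baseline elsewhere: every QTcF row in SAP 9.4.2 requires a change from baseline as well as an absolute limit. At stake is how the hepatic safety table reads. Each arm's percentage would overstate what arose on treatment, and a real relative difference would look smaller.

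**Working it through.** **Step 1: which rows can an eligible subject already meet at baseline?** Row limits are from SAP 9.2.3 and entry limits from Protocol 4.2, item 15. A row is open at entry only if there is no entry limit for that test or the entry limit lies above the row limit.

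| Row | Row limit (x ULN) | Entry limit (x ULN) | Open at entry? |
|---|---|---|---|
| AST; ALT; AST or ALT | >3, >5, >10, >20 | excluded if >3 | No |
| Total bilirubin | >2 | excluded if >2, Gilbert's exempt | Only for Gilbert's |
| ALP | >1.5 | none | Yes |
| AST or ALT with bilirubin | >3 with >1.5 or >2 | AST/ALT excluded if >3 | No |

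That is 12 transaminase rows, 1 bilirubin, 1 ALP and 2 combined, 16 in all. One is open, and a second is open to one exempted group.

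**Step 2: does another tabulation separate the cases?**
- SAP 9.2.1 gives baseline values and change from baseline by visit for selected tests. It does not show which subjects crossed a limit.
- SAP 9.2.2 is a shift table on the investigator's reading (normal, or abnormal with or without clinical significance), not on ULN multiples.
- The baseline liver function subgroups in SAP 9.1.6.2 apply to adverse events and deaths.
- The listings allow reconstruction by hand only.

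**Step 3: effect on the ALP row.** The plan gives no figure to reproduce, and all rates here are assumed. Let b be the share above the limit at baseline, r the share of those still above it after dosing, and i the new-onset rate among the rest.

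Observed rate = b x r + (1 - b) x i

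Take i = 10% and 5%, so the true ratio is 2.0 and the true difference 5.0 points. For b = 10% and r = 1:
- first arm: 0.10 + 0.90 x 0.10 = 19.0%
- second arm: 0.10 + 0.90 x 0.05 = 14.5%
- ratio 19.0 / 14.5 = 1.31; difference 4.5 points

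| b | Observed, r = 1 | Difference (points) | Ratio, r = 1 | Ratio, r = 0.7 |
|---|---|---|---|---|
| 2% | 11.8% vs 6.9% | 4.9 | 1.71 | 1.78 |
| 5% | 14.5% vs 9.75% | 4.75 | 1.49 | 1.58 |
| 10% | 19.0% vs 14.5% | 4.5 | 1.31 | 1.39 |
| 20% | 28.0% vs 24.0% | 4.0 | 1.17 | 1.22 |

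The difference equals (1 - b) x 5.0 points whatever r is, so it shrinks slowly; the ratio shrinks much faster. With the planned 300 and 150 subjects, b = 10% and r = 1 put 30 + 15 pre-existing cases in the row. Restricting the denominator to subjects at or below the limit at baseline returns 10% and 5%.

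**Step 4: no drug effect at all.** A simulation drew lognormal ALP levels for 400,000 subjects per scenario, with one baseline and three post-baseline values each. Assumptions were a median of 0.7 to 0.9 x ULN, between-subject SD of the log 0.4 to 0.7 and within-subject CV 10% to 20%. The ALP row then counts 4.7% to 31.6% of subjects. At median 0.8, SD 0.5 and CV 20% it counts 18.7%. Of those, 8.5 points were not above the limit at baseline and 18.7 - 8.5 = 10.2 points were. The 8.5 points are measurement fluctuation, which a baseline condition does not remove.

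**The case against.** The strongest reply is that the table does what it says: it reports post-baseline values and does not call them treatment-emergent or drug-caused. Protocol 8.7 makes all safety analyses descriptive. Randomization balances baseline ALP in expectation, so neither arm is favoured, and the absolute difference is little affected (4.0 to 4.9 of 5.0 points in the illustration). Baseline values, changes and listings exist elsewhere, so a reader could trace a pre-existing case. All of this stands and limits the weight of the point. It does not supply the missing split by ULN multiple.

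A reader might also infer that the whole table is affected, because the first transaminase limit and the stand-alone bilirubin limit equal the entry limits and the combined row uses bilirubin above 1.5 x ULN. The documents do not support that. An entry limit equal to the row limit keeps eligible subjects out of the row at baseline. The 1.5 x bilirubin limit appears only together with AST or ALT above 3 x ULN, which entry excludes, so a new transaminase rise is still needed even if the bilirubin part was already present. Subjects enrolled in error, or whose values changed between the eligibility sample and the last pre-dose value, could add a few cases, but that is not a defect of the rule.

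Finally, simply dropping subjects above the limit at baseline would hide real worsening, such as ALP rising from 1.6 to 5 x ULN. That objection is right and shapes the fix.

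**Conclusion.** The point holds for the ALP row, and for Gilbert's subjects in the stand-alone bilirubin row. There, elevations present at entry are counted among abnormalities after dosing, which raises each arm's rate and moves the ratio toward 1. The direction follows from the two texts, provided that elevated subjects remain above the limit more often than others newly cross it. The size does not follow: it depends on baseline prevalence and persistence, and the documents give neither figure and do not size the Gilbert's group. Across an assumed prevalence of 2% to 20%, a true ratio of 2.0 would show as 1.71 to 1.17 with full persistence, or 1.78 to 1.22 at 70%.

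It would be too strong to say that the table biases the comparison toward one arm or hides the main hepatic signal. The transaminase and combined rows are sound on this point. This is a worthwhile low-cost improvement to a descriptive table and does not touch the trial's efficacy conclusions.

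**What to change.** In SAP 9.2.3, keep the existing count of any post-baseline exceedance. For ALP and total bilirubin, add:

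1. The same count split by baseline category: at or below the row's limit, or above it.
2. A shift table per arm of baseline ULN category by worst post-baseline ULN category, so that worsening from an already elevated baseline stays visible.
3. The treatment-emergent percentage, with subjects not above the limit at baseline as the denominator.

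The baseline value is the one already defined in SAP 9.2.1. The AST, ALT and combined rows stay as they are.

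The cost is a few lines of SAP text, one extra table and denominators that differ by row. No new data are needed.

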9.3. Vital Signs

Vital signs will be summarized based on the Safety Population.

Descriptive statistics will be provided by treatment group for vital signs as follows:

- Baseline value
- Values at each post-baseline visit (nominal visit)
- Change from baseline at each post-baseline visit

A baseline value will be defined as the last available value collected on or prior to the date/time of first dose of study drug. Change from baseline for a postbaseline visit will be defined as the postbaseline value minus the baseline value. Vital signs measured at unscheduled visits before first dose will be included for the baseline value selection.

In the case of multiple values in an analysis window, data will be selected for analysis as described in Section 3.7.5.

A by-subject listing of vital signs will be provided by visit in chronological order.

9.4. Electrocardiogram Results

Electrocardiogram (ECG) analysis results are intended to identify meaningful changes in the QT interval. If potential abnormalities of interest are identified, further analyses may be conducted. Summaries of investigator assessment of ECG readings will be provided for the Safety Population for each scheduled time point.

9.4.1. Investigator Electrocardiogram Assessment

A shift table of the investigators' assessment of ECG results at each visit (nominal visit) compared with baseline values will be presented by treatment group using the following categories: normal; abnormal, not clinically significant; abnormal, clinically significant; or missing. The number and percentage of subjects in each cross-classification group of the shift table will be presented. Subjects with a missing value at baseline or postbaseline will not be included in the denominator for percentage calculation.

A by-subject listing for ECG assessment results will be provided visit in chronological order.

